
If the site does not have vaccine, we will send a message to participants due for second or third dose letting them know not to come in yet and that we will inform them when the sites have vaccine available again.

Measures

Outcome Measure: The primary outcome measure is completion of the 3-dose HPV vaccine series within 12 months from date of first dose. A secondary outcome is timeliness of vaccination, defined as time elapsed in days between dose 1 and 2, and dose 1 and 3.

Process Measures: Individual level information from the log files of the text-messaging platform will be collected to demonstrate that the correct messages were sent to each recipient for Arms 1 and 2. We will also determine the percentage of (1) text messages that sent back as undeliverable; and (2) participants opting out of the reminders during the study. We will also determine which specific vaccine health literacy-related information families request via text message, providing, in a prospective fashion, an indication of the most common parent identified HPV vaccine health literacy needs arising at the time that parents are making decisions regarding return for subsequent doses. This prospective information does not currently exist.

Follow-Up: Minimizing attrition and missing outcome data are crucial for valid results. We expect there will be little attrition with respect to outcome data. The hospital immunization registry, EzVac, automatically collects vaccine administrations from the EHR used at the 4 study sites as well as from the New York Citywide Immunization Registry (CIR) as part of the usual patient care, thereby allowing capture of vaccines administered to clinic patients both at study sites and at practices other than study sites in NY City.^{55,56} Thus, we will have outcome data for subjects who receive HPV vaccination at facilities other than a study site. A second important issue is documentation of the intervention. In our previous HPV study, no one dropped out of the study after enrollment;²⁰ in our influenza text message RCT, only 4.5% of the 9,213 families declined further messages.¹³ In addition, we expect only a small number of cell phone numbers will change over the course of the intervention. In our previous adolescent study, the number of cell phone numbers that changed was <2%.¹⁴

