Data Management: Vaccination data will be retrieved from EzVac. All data will be accessed using a password-protected computer in a locked office and stored on a secure server managed by Columbia University IT, and backed up on a daily basis. All data files will be cleaned and edited prior to analysis, under [name] supervision. Data analysis will be performed using SAS (Cary, NC). The programmer will monitor log files of text messages sent, replies received, and "undeliverable" messages and provide summaries to [name] on a daily basis.

Statistical Procedures

Data Analysis: We will first assess the randomization process by comparing baseline variables among the three groups. Hypothesis: Completion and timeliness will be higher in adolescents in families who receive enhanced text message reminders plus usual care vs. non-enhanced text message reminders plus usual care.

Series Completion: HPV vaccine completion rates in EzVac will be compared for all adolescents of participant parents at the end of a 12-month observation period starting at receipt of their first HPV vaccine dose. As in our previous RCT of influenza vaccine reminders,¹³ all primary analyses will be done on an intention-to-treat basis, such that all randomized participants will be included in the analysis whether or not they at some point declined further messages or messages were returned as undeliverable. A secondary analysis will compare completion rates for adolescents of participants who received the entire set of reminders. Study arms will not be combined. Completion rates in the two randomized groups will be compared in the separate combinations delineated above using 2-sided 2 tests at a significance level of $P<0.05$ for each comparison. The number of subjects in each cell is expected to be high enough that the Fisher exact test will not be needed. Asymptotic confidence limits on the differences and relative rate ratios will be calculated.

Sub-group Analyses: We will perform subgroup analyses in different covariate-defined subgroups, for each outcome, to assess the possibility of intervention effects being different in these subgroups. This will be tested by including pre-specified covariates (adolescent: age, gender, year of entry, clinic site, dichotomized visit count; parent: language, previous participation in text message vaccination reminder study),^{42,43,60,61,64-}

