Timeliness: We define timeliness of vaccination according to the ACIP recommended intervals.⁶⁹ We will construct Kaplan-Meier curves of time from first to second dose and separately first to third dose,⁷⁰ using both intention to treat as well as analyses accounting for message deliverability. We will then compare the curves using a log rank test. We will perform secondary subgroup analyses using Cox proportional hazards modeling to examine subgroup effects and to adjust for the same covariates as described above. Interactivity of messages: With regard to analyses pertaining to the interactive nature of messages in Arm 1, we will calculate the proportion of families who sought information about each individual topic both for the overall arm as well as subdivided by gender and parental language and stage of HPV vaccine decision-making at baseline. We will use Pearson's chi square to compare completion rates at 12

months in adolescents in Arm 1 whose families requested further information vs. those in Arm 1 who did not.

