Missing data: We will document missing data and classify it by variable and study arm. We will then assess if there are relationships between missingness and covariates such as demographics, study arm, or year of study entry. In the analysis of the study hypotheses, all randomized subjects will be included (intention to treat analysis). Missing outcome data will be imputed as failure in all study arms. We anticipate very few subjects will be missing outcome data. In the subgroup analyses, covariate data may also be missing. We will impute these variables using multiple imputation following the methodology of Rubin.⁷¹ We will achieve this using the 3-phase SAS/STAT procedure that first creates “m” multiply imputed complete data sets using the MI procedure, then analyzes the “m” complete datasets using a standard procedure, PROC LOGISTIC, and finally generates valid statistical inferences about the missing values by combining the results using the MIANALYZE procedure properly reflecting the uncertainty due to missing values. In summary, the primary analysis of the study hypotheses will be based on intention to treat analysis using all randomized subjects. Subjects with missing outcome data will be retained in the analysis; failure to complete the 3-dose series will be imputed for those missing these data. We consider this to be the most conservative approach to hypothesis testing. We used this approach in our influenza-vaccine text message reminder study.¹³ Multiple imputation will be used for the missing covariate data in subgroup analyses.

In addition as of 10/21/16: Any parents of an adolescent who was <15 years when first vaccinated who is already enrolled and has not yet received their second dose, will get a text message letting them know that there is an important update, that their child now only needs two doses with the second one being 6 months after the first and that we will text them when that dose is due. We have included that text message under documents.

Parents of adolescents first vaccinated before 15 years of age who have not yet received a second dose will receive an updated series of messages to be consistent

with the now 2 dose recommendation in both phrasing and timing (second dose now due 6 months after the first instead of 2 months and is now the last dose.

Recruitment And Consent

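### The timeliness analysis was not updated for the 10/21/16 change: who is at risk for dose 3 is unstated, and on the natural reading the unstratified dose 1-to-3 comparison is weakened by an amount that depends on an unreported two-dose share

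*Combined protocol and SAP*

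**What the plan says.** Under Measures (Outcome Measure), the secondary outcome is "timeliness of vaccination, defined as time elapsed in days between dose 1 and 2, and dose 1 and 3".

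The Timeliness paragraph of Statistical Procedures opens by tying timeliness to the ACIP intervals, without naming a version or date. It continues "We will construct Kaplan-Meier curves of time from first to second dose and separately first to third dose", by intention to treat and also by analyses that account for message deliverability. Then: "We will then compare the curves using a log rank test". No strata and no censoring time are given. Next: "We will perform secondary subgroup analyses using Cox proportional hazards modeling", using the covariates of the logistic models. Sub-group Analyses lists those covariates, which include age and year of entry, and says "We will perform subgroup analyses in different covariate-defined subgroups, for each outcome".

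The hypothesis under Data Analysis names timeliness beside completion. The Missing data paragraph says "In the analysis of the study hypotheses, all randomized subjects will be included (intention to treat analysis".

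The text dated 10/21/16, placed after Missing data, says that parents of adolescents first vaccinated before 15 "who have not yet received a second dose will receive an updated series of messages", with the "second dose now due 6 months after the first instead of 2 months and is now the last dose". It changes the phrasing and timing of messages. It does not mention the timeliness curves, the risk set for dose 3, or stratification.

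**The concern.** From 10/21/16 some randomized adolescents have families who are told that dose 2 completes the series. If they stay in the dose 1-to-3 analysis, they are counted as still awaiting a dose that no longer applies to them. Two things follow.

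- The curve's level at 12 months reflects the mix of schedules as well as how promptly three-dose adolescents return.
- An unstratified log-rank test keeps people in the risk set who will almost never have an event, which pulls the hazard ratio toward 1.

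For dose 1-to-2, due dates of 2 and 6 months share one elapsed-days axis, so a pooled curve cannot show who was on time.

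The document carries an IRB approval date of January 5, 2021, more than four years after the change. What is at stake is a secondary outcome that belongs to the stated hypothesis. The primary test and the sample size are outside this point.

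**Working it through.** **Inputs from the documents** (Study Sample and Enrollment): 478 per arm, 51% in the control arm, a 9-point difference, 80% power, 5% type I error. The test is two-sided (Series Completion).

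**The plan's own figure.** With p̄ = 0.555, n = [1.96·√(2·0.555·0.445) + 0.8416·√(0.51·0.49 + 0.60·0.40)]² / 0.09² = (1.3775 + 0.5891)² / 0.0081 ≈ 477.5, so 478 per arm. This reproduces. It is for the primary outcome; no power is stated for timeliness.

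**Assumptions.** The primary rates are carried over to dose-3 receipt by 12 months in three-dose adolescents (51% vs 60%), with proportional hazards, censoring at 12 months, and no third dose in two-dose adolescents. The two-dose share f is not in the documents, so a range is shown.

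**Ceiling of the dose 1-to-3 curve.** The control level is 51·(1−f) and the visible difference is 9·(1−f):

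| f | control level | difference (points) |
|---|---|---|
| 5% | 48% | 8.5 |
| 10% | 46% | 8.1 |
| 25% | 38% | 6.8 |
| 50% | 26% | 4.5 |

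**Power of a schedule-aware test.** HR = ln 0.40 / ln 0.49 = 1.284, and expected events are D = 478·(0.51 + 0.60)·(1−f) = 530.6·(1−f). Power is Φ(√D/2 · ln HR − 1.96), with ln HR = 0.2504:

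- f = 0: 82%
- f = 5%: D = 504, Φ(0.85) = 80%
- f = 25%: D = 398, Φ(0.54) = 70%
- f = 50%: D = 265, Φ(0.08) = 53%

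**Power with everyone pooled** (simulated, 4,000 to 6,000 runs per cell):

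| f | pooled log-rank | schedule-aware | pooled HR |
|---|---|---|---|
| 5% | 77–78% | 80% | not computed |
| 25% | 58–60% | 69–71% | about 1.24 |
| 50% | 31–36% | 53% | about 1.22 |

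The pooled ranges run from exact balance of schedule between arms to chance balance. The fall from 82% to the schedule-aware column is due to fewer dose-3 events, which no analysis recovers. Only the gap between the two power columns is due to the analysis.

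**Type I error.** With chance balance it is about 5%. With exact balance it is below 5%: the check 2·[1 − Φ(1.96/√((1−p)/(1−(1−f)p)))] with p = 0.51 gives 2.8% at f = 25% and 1.6% at f = 50%. Age group (9-14 vs 15-17) is a randomization stratum and entry date is not, so the truth should lie between the two cases.

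**What the planned Cox models recover.** All inputs here are assumed: uniform entry over 30 months; 50% under 15; the change at month 6, 15 or 24; exponential dose 2 after day 60 or 180 with 80% or 65% of controls by day 365 and HR 1.22; and 3% of two-dose adolescents still receiving dose 3. There were 1,000 runs per case, so the simulation standard error is up to √(0.25/1000) = 1.6 points.

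| change at month | planned log-rank | Cox with age and year | log-rank stratified by baseline cohort |
|---|---|---|---|
| 6 | 37% | 53% | 54% |
| 15 | 55% | 64% | 67% |
| 24 | 69% | 73% | 74% |

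Across 25, 50 and 75% under 15, the Cox model is within 0 to 3 points of the stratified test.

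**Why the schedule followed is not a safe grouping.** For those enrolled before the change, it depends on whether dose 2 had already been given. Take first doses uniform over the prior 365 days and the dose 2 model above. The control hazard is ln 5/305 = 0.00528 per day, and the share with dose 2 is (305 − 0.80/0.00528)/365 = 42%. At HR 1.22 it is (305 − 0.860/0.00644)/365 = 47%. The groups would differ by arm because of the intervention itself.

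**The case against.** The strongest reply has four parts.

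1. The ACIP sentence could carry a schedule change into the definition, and intention to treat is explained elsewhere as inclusion despite declined or undeliverable messages, which is not a statement about who is at risk for dose 3. This stands in part. The plan does not say that two-dose adolescents remain in the dose 1-to-3 curve; that is an inference. It is still the natural one, because the Timeliness paragraph itself specifies intention to treat and the all-randomized rule covers the study hypotheses. An undated reference to intervals does not settle who belongs in the risk set, and it sits uneasily with an endpoint in elapsed days.
2. The planned Cox models already do most of the work. This stands for power. Sub-group Analyses also allows interactions of covariates, and age by year would track the schedule more closely, though only if retained at p<0.05. But the Timeliness paragraph labels these models secondary subgroup analyses, and they leave the curve unchanged.
3. Approach Overview foresees analysing two doses. It does so for completion and does not carry this into timeliness.
4. At a low share the harm is small. This stands: at 5% it is 2 to 3 points of power, and the control level moves from 51% to 48%.

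A reader might infer that the test gives false positives, or that dose 1-to-2 also loses power. Neither is supported. Type I error is at or below 5%. The pooled-versus-stratified difference for dose 1-to-2 was under 1 point with one set of assumed rates and 1 to 5 points with another, so no loss is claimed.

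**Conclusion.** The point holds as a gap in specification with a real but uncertain cost. The timeliness text predates the two-dose change in substance and leaves the dose-3 risk set open. On the natural reading, the dose 1-to-3 curve has a ceiling set partly by the two-dose share. The unstratified log-rank test gives up about 2 points of power at a 5% share, 10 at 25%, and 17 to 22 at 50%, relative to a test that respects the schedule.

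These figures rest on an assumed share and on an effect borrowed from the primary outcome; the documents give neither for timeliness. It would go too far to call the dose 1-to-3 curve unreadable in all cases, since that depends on the share. Severity is low to moderate, and the change is cheap enough to make regardless of the share.

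**What to change.** Reconcile the Measures definition, the Timeliness paragraph and the 10/21/16 text. State whether timeliness means elapsed days or adherence to recommended intervals, which dated intervals apply to whom, and who is at risk for dose 3. No schedule is proposed here.

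Make the timeliness test a log-rank (and Cox) stratified by baseline cohort, with all randomized adolescents included:

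- 15-17 at first dose, any date
- under 15, first dose on or after 10/21/16
- under 15, first dose in the 12 months before 10/21/16 (transitional)
- under 15, first dose earlier than that

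Use only age at first dose and date of first dose, never the schedule actually followed. Show both dose curves by cohort, and do not pool the dose 1-to-3 curve over cohorts to whom a third dose did not apply. Label any estimate limited to the three-dose cohorts as supportive: it departs from the all-randomized rule, and in the calendar scenarios it changed power by −4 to +17 points against the planned log-rank test.

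The cost is SAP wording and a STRATA statement. Sample size is unchanged, and the first dose is given at a study site by eligibility, so its date is available. The downsides are more curves and a transitional cohort of unknown size, whose result mixes dose-3 uptake with who was switched.

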This study will be conducted in four community health clinics affiliated that are part of the New York-Presbyterian Hospital (NYP) Ambulatory Care Network (ACN) and Columbia University. These clinics are in Health Professional Shortage Areas (HPSA) and care for many families living in the Washington Heights/Inwood section of northern Manhattan.⁵³ These practices provide >55,000 visits annually; 87% for publicly insured patients, and the vast majority of families are Latino. The Vaccines for Children (VFC) Program provides the majority of vaccines given at the practices for free. Although the patient population and providers are similar across sites, baseline variability between sites will be accounted for in the randomization. All vaccinations given at the study sites are documented in the NYP Immunization Registry, EzVac, of which [name] is Medical Director. The EzVac database contains over 2.2 million vaccinations administered to >275,000 patients. EzVac extracts information about vaccinations directly from the provider order entry module of the electronic health record (EHR) making data accurate for HPV vaccines administered at the clinical sites. EzVac as part of its regular practice synchronizes data with the New York Citywide Immunization Registry (CIR) which is a population-based registry. NY City Public Health Law requires documentation for all vaccinations administered to those 18 year-olds be submitted to CIR,⁵⁴ which captures more than 85% of vaccines administered in NY City, and 93% of vaccines from the Vaccines for Children Program (VFC).^{55,56} Almost all (91.4%) adolescents at the four study sites are VFC-eligible, i.e. publicly insured or uninsured. Therefore, the few vaccines administered outside of the practice network to patients from the study sites are also captured in EzVac through this synchronization for patient care. [name] team has built a secure text messaging platform linked to EzVac. This platform allows custom text messages to be created, and sent out according to a schedule. Before a set of scheduled message is sent, the system can re-query the EzVac database to identify if patients have received the appropriate vaccination and exclude them from receiving additional reminders. The text messaging platform is designed to be interactive; patients can text a reply to stop or resume

reminders, toggle the language of messages, and ask for assistance. It is also already programmed to send and respond to interactive text messages.

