We will identify in EzVac those who received their first HPV vaccine in approximately the last week for whom we do not have a card. On inclusion, either via return of the enrollment card or over the phone, a confirmation text message will be sent to the participant family and delivery status assessed to ensure that the family has a working cellphone with text message. An undelivered message will be attempted to be delivered twice moreover the next week. If there are three undeliverable messages then the family will not be considered to have met eligibility criteria and will not be considered enrolled in the trial; they will be notified of this. We will enroll only one child per family. If more than one is eligible, we will select the one with the next most proximal birthday, e.g. a child whose birthday is in 7 days will be selected over a sibling whose is in 75 days. In the case of twins, whoever was designated at birth as twin A will be enrolled. If another adolescent becomes eligible during the trial, the family cannot re-enroll.

Randomization: Randomization will occur with a 1:1 allocation ratio stratified by (1) clinical site; (2) adolescent's gender; (3) parental language; and adolescent's age group (9-14; 15-17). These factors will be excerpted from the medical record after enrollment. Randomization will be done centrally by the programmer using an algorithm based on site, gender, language, and age. The statistician and analyst will be kept blinded to group assignment.

Study Sample and Enrollment

Based on EzVac data, there were 817 adolescents (females and males) 11-17 years old who received their first HPV vaccine at the four study sites between October 2012 and September 2013. Nearly all of those families (n=805) spoke English or Spanish. A few (n=51) were from the same family. Therefore, we expect 1885 adolescents to be eligible over the 30-month recruitment period. Across various studies conducted at the study sites, we found that between 83% and 89% of parents had text messaging. In one study, we assessed those with and without text messages and found no significant differences between those who had texting and those who did not in terms of adolescent's gender, parents' primary language, education level, or parent age. Using the low-end of this range, i.e. 83%, we expect 1,564 families to meet age, language and cell phone/texting inclusion criteria. To meet our sample size of 956 total (478 per arm), we would need to

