recruit 61.1% of eligible families. In our most recent text message vaccine related study in which we completed active recruitment, 92% of eligible patients enrolled. We therefore believe our enrollment goal is realistic. At the study sites, 35% of 11–17-year-olds who initiate HPV vaccination and receive usual care receive 3 doses within 12 months. In our previous study, we had an effect size of 16% between those receiving conventional text messages and usual care. Therefore, based on this data, we expect a completion rate of 51% in the conventional group (Arm 2). With the proposed sample size in each arm and allocation, we will be powered to detect a minimum of 9% difference between arms with 80% power, allowing for a type I error of 5% for the primary outcome. In our second dose influenza vaccine study (section D3.1), our effect size was 9% between each arm; we expect the effect size in this trial to be higher since the messages will be personalized.

Intervention and Usual Care: The study will include approximately 30 months of recruitment. The intervention period for each individual is the 12-month period starting from administration of their first dose, as is standard in studies assessing HPV series vaccine completion as well as the efficacy trials.^{37,39,50,60-62}

Arm 1: Randomized to receive additional enhanced text messages with vaccine health literacy-promoting information: An interactive query sent before the next dose is due will assess whether a parent is in the pre-contemplation stage and unaware their adolescent needs another HPV dose or when the dose is due, or if they are in the contemplation stage knowing that their adolescent needs further doses, but still undecided maybe due to questions regarding the vaccine efficacy, side effects and safety, or if they are in the preparation phase and planning to vaccinate but still in need of information on where to go or when. These will be based on previously published HPV vaccine decisional measures that used the trans-theoretical model.²⁶ Messages will then be tailored to their stage. In addition, we will include interactive text messages in the series that will allow participants to select to receive more information according to their specific needs, allowing self-tailoring of the text messaging. Finally, the current health literacy recommendations include “universal precautions” with all patients receive health literacy-promoting information regardless of perceived risk for limited health

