literacy.⁶³ Therefore, all participants in this arm will receive some text messages related to the most common HPV vaccine related health literacy needs. The text messages have been attached to the protocol.

Arm 2: Randomized to receive non-enhanced text message reminders: Will receive non-enhanced text reminders notifying them when the next dose is due. They will receive messages in parallel timing to Arm 1. These will not include vaccine health literacy-promoting information and will be similar to those used in our previous adolescent studies.^{20,14} These are also attached to the protocol. Based on our preliminary studies, all text messages will be personalized and designed to be from the patient's medical home. In our previous studies, parents indicated that they wanted their child's name on the message as well as that it was being sent on behalf of the clinic.^{16,19} The recipient will be the parent based on our previous work. We will text the cell phone number listed in the registration system, indicative of the parent who is to be contacted regarding medical care. Messages will be sent in English or Spanish based on the language preference of the participant. Throughout the study, participants will have the option to stop receiving text messages by replying to a text message with the word "quit" or "stop" in English or the corresponding commands in Spanish. Participants can request help by texting "help". They can also call the study team. These instructions will be given in a text message. After the first message sent to categorize those in Arm 1 and the parallel-timed message for Arm 2, preliminarily, we will send the first series of automated weekly reminders, beginning around d35 after the second HPV vaccine dose due date and will end two weeks after the vaccine is first over-due. Two booster doses will then be sent 28 and 42 days later, if the child has not been vaccinated. We will repeat the intervention beginning approximately d35 after second dose as a reminder for the third dose. The messages will be the same but refer to the third dose. The hospital's immunization registry will be queried before the third dose to ascertain if the patient received the second dose on time. If not, the message schedule for the third HPV vaccine dose will be readjusted for the new due date, based on CDC recommendations for minimal and desired intervals. All the study sites allow walk-ins for second and third doses of HPV vaccine, so no appointment is needed.

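### The chi-square of completion in Arm 1 requesters versus non-requesters can show a spurious gap of either sign, because the chances to request depend on dose receipt

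*Combined protocol and SAP*

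**What the plan says.** In the combined protocol and SAP, Statistical Procedures (Interactivity of messages) plans a Pearson chi-square of completion at 12 months "in adolescents in Arm 1 whose families requested further information vs. those in Arm 1 who did not". It gives no period over which requests count, no landmark, no covariates, and no restriction to families to whom the prompts were delivered. The Timeliness text just before it does plan analyses that account for deliverability.

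Other sections determine how many prompts a family gets:

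- Study Sites: before scheduled messages go out, the platform can query the registry again to "identify if patients have received the appropriate vaccination and exclude them from receiving additional reminders".
- Intervention and Usual Care: Arm 1's interactive messages sit inside the reminder series. Reminders are weekly and end two weeks after the dose becomes overdue. Two further messages, 28 and 42 days later, go only to those still unvaccinated.
- Same section: "We will repeat the intervention beginning approximately d35 after second dose as a reminder for the third dose". The second series is thus timed from receipt of dose 2.
- Missing data, addition dated 10/21/16: families of adolescents under 15 at first vaccination who still await dose 2 move to two doses, so they have no dose-3 series.

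The message texts are an attachment outside the public text. The number and placement of interactive messages are therefore not known here.

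**The concern.** On the plain reading, a family counts as a requester if it ever asked for information, over the same 12 months in which completion is judged. Each message is a chance to ask, and the number of messages follows from the vaccination history:

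- Prompt vaccination cuts a series short, so completers have fewer chances. This pushes the requester gap negative.
- Dose 2 is a precondition of three-dose completion and also opens the second series, so families lost before dose 2 have fewer chances. This pushes the gap positive.

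Exposure is then partly a consequence of the outcome process, and an unadjusted chi-square has no protection against that. Families who opt out or become unreachable also fall among the non-requesters. If families moved to two doses are still judged on three, they too combine fewer chances with certain failure.

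This is the only planned analysis that links use of the interactive content, a novel part of the intervention, to completion. A gap in either direction would invite a reading about whether asking for information helps, although it could reflect only how many prompts were sent.

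**Working it through.** **1. The plan's own figure.** The plan gives no sample size for the requester comparison. Its trial size does reproduce. Study Sample and Enrollment expects 51% completion in Arm 2 and says the trial is "powered to detect a minimum of 9% difference between arms with 80% power", at a type I error of 5%. With 51% vs 60%, two-sided:

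n = [1.96·√(2·0.555·0.445) + 0.842·√(0.51·0.49 + 0.60·0.40)]² / 0.09² = (1.378 + 0.589)² / 0.0081 ≈ 478 per arm, as stated.

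Arm 1 is therefore taken as 478 families with 60% completing.

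**2. Formula under the null.** Let every prompt have the same request chance q, whatever the outcome, and let requests have no effect. With m prompts, P(ever request) = 1 − (1 − q)^m. Write R_C for completers, R_N for non-completers and c for completion. Then

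- completion in requesters = c·R_C / [c·R_C + (1 − c)·R_N]
- completion in non-requesters = c·(1 − R_C) / [c·(1 − R_C) + (1 − c)·(1 − R_N)]

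The gap is zero only if R_C = R_N. The value of q, the number of interactive messages, the dose dates and the point at which non-completers drop out are assumptions.

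**3. A positive gap.** One interactive prompt per series, q = 0.30, all non-completers lost before dose 2. R_C = 1 − 0.7² = 0.51 and R_N = 0.30.
- Requesters: 0.306 / (0.306 + 0.120) = 71.8%
- Non-requesters: 0.294 / (0.294 + 0.280) = 51.2%
- Gap: +20.6 points

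If only half of the non-completers miss dose 2, R_N = 0.405 and the gap is 65.4% − 55.3% = +10.1. If all of them receive dose 2, R_N = R_C and the gap is 0.

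**4. A negative gap.** Eight interactive messages per series (six weekly, two later), q = 0.10, doses at d60–75, all non-completers stopping after dose 2. Simulated mean prompts are 10.3 for completers and 13.1 for non-completers. R_C ≈ 1 − 0.9^10.3 = 0.662 and R_N ≈ 1 − 0.9^13.1 = 0.748.
- Requesters: 0.397 / 0.697 = 57.0%
- Non-requesters: 0.203 / 0.303 = 66.8%
- Gap: about −9.8 points (−10.2 in full simulation)

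**5. Simulated range.** Null simulation with 400,000 families per scenario for the gap and 600 samples of 478 for the share of trials with p<0.05. Completion is 60%. The first series is read as starting at d35 after dose 1, with dose 2 due about d60.

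| Scenario | No non-completer misses dose 2 | Half miss it | All miss it |
|---|---|---|---|
| 8 interactive, doses d60–75, q=10% | −10.2 (52%) | 0.0 (4%) | +9.6 (54%) |
| 8 interactive, doses d60–130, q=10% | −5.3 (18%) | +7.4 (31%) | +18.6 (98%) |
| 8 interactive, doses d60–200, q=10% | −2.7 (8%) | +11.7 (63%) | +23.8 (100%) |
| 1 interactive per series, q=30% | +0.1 (5%) | +10.1 (65%) | +20.6 (99.5%) |

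If the only chance to request is one query before dose 2 is due, the gap is about 0 (+0.2).

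**6. Check on the error rates.** With 40% requesting, SE = √[0.6·0.4·(1/191 + 1/287)] ≈ 4.6 points. A spurious 4-point gap is then significant about 14% of the time and an 8-point gap about 42%, against a nominal 5%.

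**7. Check on the remedy.** Classifying by requests before d60, when no dose 2 had yet been given in the simulation, brought every gap within ±0.4 points, with rejection rates of 3.7% to 7.8%, mostly 4% to 6%. In a further null simulation, a time-varying request term in one dose 1 to dose 3 Cox model still gave spurious hazard ratios of 1.09 to 1.78. Models fitted separately by dose interval gave 1.0.

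**The case against.** The strongest reply is that the plan never says requests are counted over the whole follow-up. With an early window, or a single prompt before dose 2, the problem disappears. That is right, and it is why the claim is that the test can mislead, not that it must. It does not rescue the plan, because the window is undefined and the interactive items are described as part of a series that is repeated after dose 2.

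Second, the sizes are scenario output. Giving every family the same independent chance at each message makes message count matter most. With requests clustered within families (intraclass correlation 0.3, itself an assumption), gaps of −5.9, +7.0 and +18.0 points on a similar schedule shrank to −1.7, +2.1 and +6.3. The bias shrinks but does not vanish.

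Third, no section presents this comparison as a test of interactivity. The hypothesis is the randomised contrast of Arm 1 with Arm 2, and Process Measures gives the purpose of request data as showing what parents want to know. This stands and limits the severity.

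Fourth, opt-outs and changed numbers should be few. Delivery is confirmed at enrolment, and Follow-Up cites 4.5% declining further messages and under 2% changed numbers in earlier studies. This stands, so that part of the concern is minor.

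**Conclusion.** The concern holds in a limited form. The mechanism follows from the plan's message rules, and under a strict null it produces gaps of both signs, from about −10 to +24 points in the scenarios shown. The two forces can also cancel. Size and sign rest on the request rate, the number and placement of interactive messages, dose timing and where non-completers drop out, none of which the documents give.

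A reader might infer more, in three ways that the documents do not support:

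- That the comparison is bound to be biased in a predictable direction. The text does not supply the inputs needed to say so.
- That the sign is set by whether reminders start before or after the due date. The sentence on the first series' start is hard to reconcile with itself and should be clarified, but both signs appear above with that start held fixed.
- That the trial's main finding is compromised. This is a secondary, non-randomised comparison within one arm, and the intention-to-treat result and the 478 per arm are untouched.

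The change is worth making before analysis, but it is not critical to the trial.

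**What to change.** Replace the chi-square with a landmark comparison:

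- Fix in advance a day after the first dose-2 interactive prompts.
- Include Arm 1 families to whom those prompts were delivered and who are still due for dose 2 on that day.
- Classify them by requests made before that day.
- Compare later dose-2 receipt and series completion, adjusted for decision stage and the stratification factors (site, gender, language, age group).
- State how families moved to the two-dose schedule enter, since their prompts fall at a different time and they have no dose-3 series.

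Alternatively, use request as a time-varying covariate in Cox models fitted separately for dose 1 to 2 and dose 2 to 3, restarting the clock at dose 2. A single dose 1 to 3 model should not be used. The SAP should say whether a request in the first interval carries into the second.

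Either way, report an association. Neither approach removes self-selection of requesters by motivation or worry.

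The cost is SAP wording and minor programming from message logs that the plan already collects. The landmark version has fewer families and less precision, and it does not use requests made in the dose-3 series, so it answers a narrower question.
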